Evaluation of *In Vitro* Cross-Reactivity with Avian Influenza H5N1 Virus in Healthy Volunteers Vaccinated with a Prime Boost Regimen of Seasonal Influenza Vaccine

Version Number: 6.0

Short Title: Cross-reactivity of prime boost seasonal influenza vaccine

Protocol Number WRAIR #1525 HRPO Log #15223

Date: 29 April 2011

1. Study Summary

Objectives

The primary objectives of this study are:

- 1. To establish whether a prime boost strategy using seasonal LAIV and IIV can augment cross-reactivity with H5N1 and human influenza strains.
- 2. To detect the presence of antibodies that can inhibit infection with H5N1 and human influenza strains in microneutralization, plaque reduction and H5 pseudotyped lentiviral particle-based assays after vaccination with seasonal LAIV and IIV.
- 3. To establish the breadth of antibody responses to H5N1 strains and human influenza strains using ELISA, microneutralization, plaque reduction, H5 pseudotyped lentiviral assays, neuraminidase inhibition assay, and hemagglutination inhibition after vaccination with seasonal LAIV and IIV.
- 4. To observe T-cell responses following vaccination with seasonal LAIV and IIV.
- 5. To attempt to generate human monoclonal antibodies that are cross-reactive to enzyme neuraminidase and hemagglutinin of H5N1 and pandemic H1N1 2009 in order to investigate further the human response to influenza vaccination

Secondary objectives are to describe the adverse event profile of 2 doses of influenza vaccine given approximately 8 weeks apart in healthy adult volunteers.

Subject Population

Subjects will be healthy adult U.S. citizens residing in Bangkok. FluMist® vaccine is not yet licensed for use in Thailand; hence Thai subjects will not be recruited into this study.

Study Site

The *in vivo* phase of the study will take place at the U.S. Embassy Medical Unit, Bangkok, Thailand. In selected cases individuals may elect to have scheduled follow-up visits (which do not involve vaccination) performed at AFRIMS. Immunology testing will be done at the Department of Immunology and Medicine, AFRIMS and the Faculty of Medicine, Siriraj Hospital, Bangkok.

Number of Subjects

Up to 34 subjects will be recruited: 26 subjects for randomization and a further 8 to act as replacements in case of drop-outs.

Vaccines Administered

Subjects will be randomized to receive one of the following 4 regimens. For each regimen the two doses of vaccine will be separated by 8 weeks (\pm 7 days).

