To detect antibodies that inhibit infection of cells with influenza virus, microneutralization assays will be performed using Madin-Darby canine kidney (MDCK) cells. Serum and nasal wash samples will be heat-inactivated (30 min at 56°C) and serial dilutions will be pre-incubated with H5N1 virus or swine flu H1N1 2009 in 96 well plates. After 1-2 h incubation at 37°C in a 5% CO2, 100 μ l of MDCK cells at 1.5 x 105 /ml will be added to each well and the plates will be incubated for 18 hours. MDCK monolayers will be washed with PBS and fixed in cold 80% acetone for 10 min. The presence of viral protein will be detected by ELISA with a monoclonal antibody to the influenza A NP. The second antibody conjugated with peroxidase will be added and incubated for another 1 h. Plates will be washed, and specific enzyme substrate will be added. The reaction will be stopped with 1 N sulfuric acid. The absorbance will be measured at 490 nm. The average A490 will be determined for quadruplicate wells of virus-infected (VC) and –uninfected (CC) control wells, and a neutralizing endpoint will be determined by using a 50% specific signal calculation. The endpoint titer will be expressed as the reciprocal of the highest dilution of

serum with A490 value less than X, where X = [(average A490 of VC wells) - (average A490 of CC wells)]/2 + (average A490 of CC wells). Sera which tested negative at a dilution of 1/20 will be assigned a titer of 10. The assay will be performed in the BSL3 lab, Mahidol University.

VI.10.2.5. Neuraminidase inhibition assay

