In addition there will be an in-house study monitor assigned to this study to ensure compliance with GCP/ICH standards. Monitoring will consist of a pre-study site visit, regular monitoring visits and a post-study visit.

XII. STATISTICAL METHODS

XII.1. Sample Size and Power

This is a descriptive study designed to detect trends in safety and immune responses that would warrant expanded investigations of potentially promising combinations {Lancaster, 2004} {Browne, 1995}. The sample size of 8 subjects in arms 3 and 4 and 5 in arms 1 and 2 is in the range of what is considered adequate for phase I trails and is not based on sample size and power calculations {Stephenson, 2005} {Lin, 2006} {Nicholson, 2001}.

Recruitment of subjects is likely to be affected by the limited number of US citizens resident in Bangkok who fulfill the eligibility criteria. Hence there will be no stratification of enrolment based on gender; this and other possible confounders (such as prior receipt of influenza vaccines) can be addressed in future large-scale trials.

XII.2. Study Outcome Analysis

Primary Analysis

Immunological data and other continuous variables will be expressed as geometric means and standard deviations if the data are normally distributed, and the vaccine groups compared using parametric tests. If not normally distributed they will be expressed as medians and the range and interquartile range given; comparison between groups will then be by non-parametric tests.

Secondary Analyses

In vivo (AE) data will be analyzed as follows: categorical data will be presented using counts and percentages, whilst continuous variables will be presented using the mean, (standard deviation) or median (range and interquartile range), and number of subjects. Percentages will be rounded to a maximum of one decimal place. All statistical tests will be performed using a 5% significance level, leading to 95% confidence intervals. Differences in incidence of reported AEs between doses and vaccines will be determined. Statistical analyses will be carried out in-house using Stata 10.0 (College Station, Texas).

XIII. ETHICAL CONSIDERATIONS

XIII.1. Study Approval

Scientific approval for this study will be obtained from the Scientific Review Committee at AFRIMS. Ethical approval will be sought from the WRAIR IRB (FWA 00000015) and the USAMRMC ORP HRPO. This study will be governed by ICH GCP guidelines.

XIII.2. Risks and Benefits of Participating

Benefits

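### Section XII.2 ties geometric means and parametric tests to normally distributed data without naming the log scale, and lets a normality judgement on small groups choose the summary and test for the titre endpoints.

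*Protocol*

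**What the plan says.** Section XII.2, Primary Analysis, sets one rule for immunological data and for all other continuous variables: "Immunological data and other continuous variables will be expressed as geometric means and standard deviations if the data are normally distributed", with the vaccine groups then compared parametrically. The alternative is "If not normally distributed they will be expressed as medians and the range and interquartile range given", and "comparison between groups will then be by non-parametric tests". The rule does not state the scale on which normality is judged, the check to be used, or whether it applies per arm, pooled, per assay or per visit. No other section mentions a log transformation for analysis.

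Six of the nine primary endpoints in section VI.1 are titres: ELISA, hemagglutination inhibition, microneutralization, neuraminidase inhibition, plaque reduction and the H5 pseudotyped particle assay. Serum is taken at six visits (Days 0, 14, 28, 56, 70 and 84). The pseudotyped assay uses two-fold dilutions (VI.10.2.7). Microneutralization has a floor: "Sera which tested negative at a dilution of 1/20 will be assigned a titer of 10" (VI.10.2.4).

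Section XII.1 gives the arm sizes ("The sample size of 8 subjects in arms 3 and 4 and 5 in arms 1 and 2") and says that the size "is not based on sample size and power calculations". Under Secondary Analyses, XII.2 adds: "All statistical tests will be performed using a 5% significance level, leading to 95% confidence intervals". The same paragraph summarises continuous adverse event data with an ordinary mean and SD.

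**The concern.** The condition and the summary do not belong together. If the titres themselves are normal, the arithmetic mean goes with the SD. If their logarithms are normal, the geometric mean goes with a geometric SD or a back-transformed interval. The text takes the condition from the first case and the mean from the second, and leaves the kind of SD open. For the other continuous variables under the same rule, normality gives no reason to use a geometric mean.

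The choice of summary is also data-dependent. With 5 to 8 subjects per arm, a normality judgement has little power to detect skew. Near an assay floor it can fail even on the log scale. One antibody curve could then be shown as a geometric mean at one visit and a median at another, which weakens the planned comparison with baseline. In a descriptive study the summaries are the main product, so this matters even without a power claim.

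**Working it through.** **Inputs from the protocol.** Arms of 8, 8, 5 and 5; floor of 10 in microneutralization; two-fold steps in the pseudotyped assay; 5% level. Check: 8 + 8 + 5 + 5 = 26, and 26 + 8 = 34, agreeing with "26 subjects for randomization and a further 8 to act as replacements in case of drop-outs". The protocol states no power, effect size or SD, so there is no power figure to reproduce.

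**Assumptions, not in the protocol.** Log-normal titres; between-subject log2 SD 1.5 (range 1.0 to 2.0); a true 4-fold difference; Shapiro-Wilk at 0.05 per arm on raw titres. If both arms pass, a t-test on raw titres; otherwise an exact Mann-Whitney test.

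**Step 1: mismatch of mean and SD.** For a log-normal variable, mean = GM × exp(σ²/2) and SD = mean × √(exp(σ²) − 1). With log2 SD 1.5, σ = 1.5 × ln 2 = 1.04 and σ² = 1.08. For an illustrative geometric mean of 80:
- mean = 80 × 1.717 = 137
- SD = 137 × √(2.948 − 1) = 192

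A literal report would read 80 with SD 192, and 80 − 192 is negative. The matching geometric SD is 2^1.5 = 2.83, a spread from 80/2.83 = 28 to 80 × 2.83 = 226.

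**Step 2: how often log-normal titres pass as normal on the raw scale** (4,000 simulated arms per setting, continuous titres; joint columns from 2,000 runs).

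| log2 SD | n = 5 | n = 8 | both arms, 5 v 8 | both arms, 8 v 8 |
|---|---|---|---|---|
| 1.0 | 85% | 70% | 60% | 50% |
| 1.5 | 75% | 51% | 38% | 26% |
| 2.0 | 64% | 34% | 21% | 12% |

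Pooling residuals over all 26 subjects, the pass rates are 35%, 13% and 4%.

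**Step 3: switching of the summary.** With two-fold steps and a floor of 10 (log2 SD 1.5), judged on the log scale, titres centred at 80 pass in 80% of arms of 5 and 81% of arms of 8. Centred at 20, they pass in only 39% and 26%. Naming the log scale alone would therefore not stop the switch between geometric mean and median.

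**Step 4: power for a 4-fold difference** (2,000 runs per setting, continuous titres).

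| log2 SD | Arms | Two-stage rule, raw scale | Log t-test | Mann-Whitney fixed in advance |
|---|---|---|---|---|
| 1.0 | 5 v 8 | 82% | 90% | 86% |
| 1.5 | 5 v 8 | 46% | 58% | 53% |
| 2.0 | 5 v 8 | 29% | 35% | 32% |
| 1.0 | 8 v 8 | 95% | 96% | 95% |
| 1.5 | 8 v 8 | 67% | 69% | 66% |
| 2.0 | 8 v 8 | 45% | 47% | 44% |

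Separate simulations at SD 1.5, 5 v 8, gave 44% to 46% for the rule and 55% to 58% for the log t-test, so about 45% v 56%.

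**Step 5: where the loss goes away (SD 1.5).**
- Normality judged on log titres, 5 v 8: 57.4% under the rule v 57.6% for the log t-test.
- Two-fold steps and floor, lower arm centred at 10: 42% v 41% (5 v 8) and 58% v 60% (8 v 8).
- The same, lower arm centred at 40: 46% v 55% (5 v 8) and 65% v 68% (8 v 8).

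**Step 6: false positives.** With no true difference, the two-stage rule rejected in 4.4% to 5.6% of runs in every setting.

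**The case against.** The strongest reply is that the choice of a geometric mean itself suggests the authors were thinking on the log scale, and that the SD may be meant as a geometric SD. On that reading the geometric mean and the parametric test agree, and Step 5 shows no power loss. How normality is checked is a detail that an analysis plan usually supplies. Near the floor, which is plausible for H5N1 in subjects thought to be unexposed, the switch to rank tests works well. Not all titres are discrete either: ELISA titres are calculated at a fixed optical density. The study is a descriptive pilot without a power target.

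Much of this stands, and it limits the size of the point. It does not remove the point. The log scale is nowhere stated, the condition as written is the wrong one for a geometric mean, and the rule also covers variables that are not titres. A log-scale reading still leaves the switching shown in Step 3.

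A reader might infer that the plan commits to raw-scale t-tests, which have only about 22% power at SD 1.5 in 5 v 8. The documents do not support that: no scale is named, and that figure is for a t-test applied regardless of any normality check, which is not the plan's rule. Nor do they state a formal per-arm test; Shapiro-Wilk is used here only for illustration.

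**Conclusion.** The rule in XII.2 is wrong as written on scale, and the point is of moderate weight. What is certain from the text is the mismatch between condition and summary, and the data-dependent choice between two summaries for the main endpoints. The power cost is conditional on the assumptions listed above: about 11 points in 5 v 8 at log2 SD 1.5 (6 to 11 over SD 1.0 to 2.0), and 1 to 2 points in 8 v 8. The 5 v 8 case is relevant because comparing heterologous with same-vaccine regimens is the stated approach (IV.2.6). There is no excess of false positives, and the non-parametric route can still reach 5%: the smallest exact two-sided Mann-Whitney p is 2/252 = 0.008 for 5 v 5. A reader might take this as a defect that invalidates the primary analysis; in an unpowered pilot, with these results, it does not.

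**What to change.** For titres, replace the rule in XII.2 with wording such as:

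> Titres are analysed as log2(titre), with values below the first dilution set to half of it. Geometric means with geometric SD or back-transformed 95% confidence interval are reported for every arm, assay and visit. Arms are compared on the log2 scale by a test fixed in advance, with an exact rank test as sensitivity analysis.

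For continuous variables that are not titres, use the arithmetic mean (SD) or the median. The half-dilution rule agrees with the microneutralization section, where 1/20 leads to 10. No new responder endpoint is needed.

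The cost is a change of wording in XII.2; no new data or visits. It is not wholly free, however. Section IV.7 reports that preliminary data from this study had already been examined, so the amendment should state that the change was made after that look.

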Arm 1: FluMist® live, intranasal vaccine 0.2mL (0.1mL per nostril): 2 doses separated by 8 weeks (±7 days); n=5 subjects. Autologous prime boost regimen 1.

- Arm 2: Fluzone® inactivated influenza virus vaccine 0.5mL intramuscularly: 2 doses separated by 8 weeks (+7 days); n=5 subjects. Autologous prime boost regimen 2.
- Arm 3: FluMist® live, intranasal vaccine 0.2mL (0.1mL per nostril) single dose, followed by Fluzone® inactivated influenza virus vaccine 0.5mL intramuscularly 8 weeks (±7 days) later; n=8 subjects. Heterologous prime boost regimen 1
- Arm 4: Fluzone® inactivated influenza virus vaccine 0.5mL intramuscularly single dose, followed by FluMist® live, intranasal vaccine 0.2mL (0.1mL per nostril) 8 weeks (±7 days) later; n=8 subjects. Heterologous prime boost regimen 2

Study Design and Methodology

This will be a randomized, open-label, pilot feasibility study of four 2-dose vaccine regimens using two commercially available seasonal influenza vaccines to compare immune responses and *in vitro* cross-reactivity against H5N1. Vaccine doses will be spaced by approximately 8 weeks to allow for optimal prime boost conditions. Humoral, cellular and secretory immune responses will be measured 2 and 4 weeks after each vaccine dose and compared with baseline values.

Study Endpoints

The primary study endpoints will be determination of pre and post vaccination immune responses in 26 healthy human subjects to 2 doses of seasonal influenza vaccine including whether there is *in vitro* cross-reactivity against H5N1 virus as follows:

- 1) Antibodies ELISA titers calculated as the dilution factor required to give an optical density of 0.5.
- 2) Hemagglutination inhibition activity defined as the titer required to completely inhibit hemagglutination);
- 3) Microneutralization assay endpoint titer; determined by using 50% specific signal calculation. The endpoint titer will be expressed as the reciprocal of the highest dilution of serum with A490 value less than X, where X = [(average A490 of VC wells) – (average A490 of CC wells)] / 2 + (average A490 of CC wells).
- 4) Neuraminidase inhibition assay titer defined as the highest sample dilution that produces 50% inhibition of virus control.
- 5) Plaque reduction assay titer assessed as the highest sample dilution that will give a reduction of plaque count of 50%.

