To date (28 May 2008), 383 cases have been reported of which 241 resulted in death (www.who.int). These represent only laboratory-confirmed cases of H5N1 infection and actual numbers might be higher. Still, the number of human cases is limited if the continued high circulation in wild and domestic birds is taken into account. Human-to-human transmission was probably only involved in a minority of cases. Even so, pandemic preparedness is necessary, since there is no doubt that an influenza pandemic will occur and rapidly changing H5N1 viruses are prime candidates to cause this pandemic {Webster, 2006}. Of great concern is the potential of reassortment of H5N1 with human viruses and/or adaptation of H5N1 to the human host that would result in a pandemic strain that can be transmitted from human-to-human. Combined with the high mortality of H5N1 (61%), this could cause a global catastrophe.

IV.2.3. Immune responses to influenza virus

The immune system recognizes and fights any incoming pathogen. It consists of two parts, the humoral immune system responsible for antibody production and the cellular immune system, including cytotoxic T lymphocytes that kill infected cells. For the resistance to and recovery from influenza, antibodies are the most important {Cox, 2004}. During the course of infection, antibodies are produced against a variety of influenza antigens, of which HA-specific antibodies are the most effective for neutralization of the virus and thus prevention of illness. However, antibodies directed against other influenza proteins can limit viral replication and ameliorate disease. After natural infection, a protective serum antibody response (haemagglutination inhibition titre \geq 40) can be detected in about 80% of subjects and the level of serum antibodies correlates with resistance to illness following natural and experimental infection {Cox, 2004}. The major neutralizing antibodies are of the IgA class, but also IgM and IgG antibodies are detected after infection. Locally, in mucosal tissues, IgA is most prominent, whereas in serum IgG levels are dominant. Antibody levels peak after 2 weeks and then begin to decline.

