Compared to IIVs, LAIVs induce a similar frequency of systemic vaccine reactions and a similar efficacy in preventing influenza {Beyer, 2002}. Serum levels of anti-influenza antibodies were lower, whereas mucosal IgA levels were higher as compared to IIVs. Unlike IIV, no general immune correlates of protection have been established for LAIV {Ambrose, 2006}. As observed for natural infections, not all differences in protection could be accounted for by differences in serum antibody titers indicating that multiple immune mechanisms confer resistance to influenza. The presence of an antibody response is predictive of protection; however, the absence of antibodies does not reflect the absence of protection. Of note, LAIVs induce broader antibody responses, not only to HA proteins but also to other influenza proteins {Ambrose, 2006 38} {Belshe, 2004}. Even, responses are not limited to the strains used for vaccination, but neutralizing antibodies are also induced that cross-react with mismatched strains. Five different efficacy trials have demonstrated that immunization with LAIV can protect against antigenically drifted influenza strains, in addition to providing protection against the influenza strains used in the vaccine {Belshe, 2004}. This was confirmed in vitro, by testing sera on antigenically mismatched strains; vaccination with LAIV resulted in antibodies to drifted variants whereas IIV could not induce such cross-reactive antibodies. These results were obtained using antigenically drifted influenza strains within the same subtype (variants of H3N2); no results are available for antigenically shifted strains (e.g. H5N1). In contrast to IIV, LAIV not only generates antibody responses, but also cytotoxic T cell responses.

IV.2.6. Vaccines against avian influenza H5N1

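### XII.2 compares the four vaccine groups as they stand; the 2x2 heterologous-minus-autologous contrast, already available in the design, would isolate the prime-boost effect at no cost

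*Protocol*

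**What the plan says.** Under Primary Analysis, XII.2 has normally distributed immunological data summarised by geometric means, "and the vaccine groups compared using parametric tests". Otherwise medians are given and "comparison between groups will then be by non-parametric tests". No contrast, reference arm or time point is named. A line under Secondary Analyses, worded to cover every test, reads: "All statistical tests will be performed using a 5% significance level, leading to 95% confidence intervals".

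XII.1 gives the group sizes: "The sample size of 8 subjects in arms 3 and 4 and 5 in arms 1 and 2". By dose order these are LAIV-LAIV (Arm 1, 5), IIV-IIV (Arm 2, 5), LAIV-IIV (Arm 3, 8) and IIV-LAIV (Arm 4, 8). XII.1 describes a descriptive study looking for trends "that would warrant expanded investigations of potentially promising combinations", with no power calculation.

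On timing, the Study Summary says: "Humoral, cellular and secretory immune responses will be measured 2 and 4 weeks after each vaccine dose and compared with baseline values". Under VI.10.1.3 the visits after dose 2 are Days 70 and 84. On the two vaccines, IV.2.5 says of LAIV: "Serum levels of anti-influenza antibodies were lower, whereas mucosal IgA levels were higher as compared to IIVs". Section V makes augmentation of cross-reactivity by prime-boost the first primary objective. The end of IV.2.6 gives the intended comparison as two doses of one vaccine against LAIV then IIV, or the reverse.

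**The concern.** At Days 70 and 84, Arms 2 and 3 are 2 to 4 weeks past IIV, and Arms 1 and 4 are 2 to 4 weeks past LAIV. If the vaccines differ in the response they raise, arms given different vaccines will differ whether or not priming with one changes the response to the other. By the protocol's own account the difference runs one way in serum and the other way in nasal IgA.

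A result such as Arm 3 above Arm 1 in serum is a valid randomized difference between regimens. It does not answer Objective 1, because one extra IIV dose would produce it. A four-group test has the same weakness: it rejects for any difference among arms, including a plain LAIV/IIV difference. The rank-based fallback compares the same groups and inherits the problem. At stake is whether a combination is carried forward as evidence of prime-boost when the data show only which vaccine was given, and when.

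**Working it through.** **Design check.** 5 + 5 + 8 + 8 = 26, the stated number randomized, and 26 + 8 replacements = 34, the stated maximum recruited. IIV is the last vaccine in 8/16 heterologous and 5/10 autologous subjects, which is half in each. There is no power figure to reproduce.

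**Additive model, no prime-boost effect.** Let I and L be the log2 rises soon after IIV and LAIV, and r the share of the first rise still present after dose 2. The arm means are:
- Arm 1 (LAIV-LAIV): rL + L
- Arm 2 (IIV-IIV): rI + I
- Arm 3 (LAIV-IIV): rL + I
- Arm 4 (IIV-LAIV): rI + L

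The contrast [(Arm 3 + Arm 4) - (Arm 1 + Arm 2)]/2 is then exactly 0 for any I, L and r. Single differences are not: Arm 3 - Arm 1 = I - L, and Arm 3 - Arm 2 = r(L - I).

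**Assumed inputs, none in the protocol.** I = 2 to 3, L = 0.5 to 1, r = 0.50 to 0.75, SD = 1 to 1.5 log2; two-sided 5%.

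Example, I = 2, L = 1, r = 0.5: the means are 1.5, 3, 2.5 and 2, and the contrast is (2.5 + 2 - 1.5 - 3)/2 = 0.

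Arm 3 v Arm 1 has standard error SD x sqrt(1/8 + 1/5) = 0.570 SD.
- Smallest signal: 1/(1.5 x 0.570) = 1.17 standard errors, rejection 19%.
- Largest signal: 2.5/(1 x 0.570) = 4.39 standard errors, rejection 98%.

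Rejection rates over the whole grid, true prime-boost effect zero:

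| Comparison | Rejects |
|---|---|
| Four-group ANOVA | 23% to over 99% |
| Arm 3 v Arm 1 | 19-98% |
| Arm 3 v Arm 2 | 8-85% |
| 2x2 contrast | 4.7-5.2% |

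Arm 3 v Arm 2 shares its last vaccine but is not clean, because the retained first-dose response differs.

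**Simpler null, last vaccine only.** With a last-vaccine effect of 0.5 to 2 SD and nothing else, the four-group test rejects in 15-98%, Arm 3 v Arm 1 in 12-90% and Arm 3 v Arm 4 in 16-96%. The 2x2 contrast rejects in 5.0-5.2%. The plain 16 v 10 pool falls from 5.1% with no last-vaccine effect to 0.5% at 2 SD, so it is conservative.

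**Power for a true 1 SD heterologous effect.** The contrast has standard error SD x sqrt[(1/5 + 1/5 + 1/8 + 1/8)/4] = 0.403 SD, and 1/0.403 = 2.48. On 22 degrees of freedom that gives about 66%, whatever the vaccine difference. The unadjusted 16 v 10 pool has 56%, 33% and 11% when the second vaccines differ by 1, 2 and 3 SD, because that difference stays in its error term.

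**The case against.** **A reader might infer that prime-boost is confounded with the last vaccine.** It is not. The arms are a randomized, complete 2x2, the last vaccine is balanced between heterologous and autologous subjects, and the comparison described in IV.2.6 is unbiased if simply pooled. This part of the objection stands in full.

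**XII.2 mandates neither an ANOVA nor Arm 3 v Arm 1, and contrasts are often left to an analysis plan.** Nothing in the text prevents the right contrast, and a plan not seen here may name it. That limits the weight. But the protocol does state a primary comparison, of the groups themselves, and that statement does not carry through the comparison in IV.2.6.

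**The background text is thin support for the sizes used.** The statement "Antibody levels peak after 2 weeks and then begin to decline" describes natural infection, not decay after either vaccine. IV.2.5 gives no magnitude. For drifted strains it credits LAIV with cross-reactive antibody that IIV did not raise, and it reports no data for shifted strains such as H5N1. The assumed serum direction may therefore not hold for H5N1. This stands against the figures. The argument itself needs only that the vaccines differ, in either direction.

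**A pilot may choose a regimen on observed response, whatever the mechanism.** That is fair for choosing a regimen. It does not cover a claim that prime-boost augments the response, which is Objective 1.

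**Conclusion.** The point holds as an inexpensive improvement of modest weight. The comparison worded in XII.2 does not isolate the effect in Objective 1, while a contrast that does is available from the same 26 subjects and the scheduled samples. With no prime-boost effect, the four-group test could reject in 23% to over 99% of trials and Arm 3 v Arm 1 in 19-98%, against about 5% for the contrast. Those ranges depend on additive effects on the log scale and on assumed rises, retention and SD. The direction of the vaccine difference has support in IV.2.5 for antibody in general, but not for H5N1.

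Two stronger readings are not supported. The design is not confounded, so no arm or sample needs changing. Nor do the pairs sharing a last vaccine (Arm 3 v 2, Arm 4 v 1) give clean prime-boost estimates on their own; they do so only if nothing of the first response persists.

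**What to change.** In XII.2, state that the Objective 1 estimate, on log titres after dose 2 (Days 70 and 84), is the heterologous-minus-autologous contrast [(Arm 3 + Arm 4) - (Arm 1 + Arm 2)]/2, with its 95% confidence interval. It comes from a model with terms for first vaccine, second vaccine and heterologous/autologous. Report every single arm pair, including Arm 3 v 2 and Arm 4 v 1, as a description of regimens only.

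Do not add comparisons of post-boost levels with first-dose levels of the same vaccine: the boosted arm also carries what remains of its prime, so they would differ without any prime-boost effect.

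The cost is a change of wording, with no new visits, samples or subjects. The downside is that fewer arm differences can be cited as evidence of a prime-boost effect.

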We propose to attempt to produce human monoclonal antibodies from the original samples collected from those subjects with high responses to allow for further analysis of the immune response to influenza vaccines. Subjects will be re-contacted to assess willingness to participate in an additional blood sampling under a minimal-risk human use protocol. A greater understanding of cross-reactive memory B cell responses to influenza neuraminidase and hemagglutinin may eventually lead to new/novel preventive and therapeutic strategies.

V. OBJECTIVES

The hypothesis to be tested in this study is that heterologous prime-boost vaccination of healthy adults with a prime boost regimen of trivalent LAIV (FluMist®) and trivalent IIV (Fluzone®) will induce cross-immunity to a variety of H5N1 avian influenza viruses and human influenza viruses.

Therefore the primary objectives of this study are:

- 1. To establish whether a prime boost strategy using seasonal LAIV and IIV can augment cross-reactivity with H5N1 and human influenza strains.
- 2. To detect the presence of antibodies that can inhibit infection with H5N1 and human influenza strains in microneutralization, plaque reduction, or H5 pseudotyped lentiviral particle-based assays after vaccination with seasonal LAIV and IIV.
- 3. To establish the breadth of antibody responses to H5N1 strains and human influenza strains using ELISA, microneutralization, plaque reduction, H5 pseudotyped lentiviral particlebased assays, neuraminidase inhibition assay, and hemagglutination inhibition after vaccination with seasonal LAIV and IIV.
- 4. To observe T-cell responses following vaccination with seasonal LAIV and IIV.
- 5. To attempt to generate human monoclonal antibodies that are cross-reactive to enzyme neuraminidase and hemagglutinin of H5N1 and pandemic H1N1 2009 in order to investigate further the human response to influenza vaccination

Secondary objectives are to describe the adverse event profile of 2 doses of influenza vaccine given approximately 8 weeks apart in healthy adult volunteers.

VI. METHODS

VI.1. Study Endpoints

The primary study endpoints will be determination of pre and post vaccination immune responses in 26 healthy human subjects to 2 doses of seasonal influenza vaccine including whether there is *in vitro* cross-reactivity against H5N1 virus as follows:

- 1. Antibodies ELISA titers calculated as the dilution factor required to give an optical density of 0.5.

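### The primary endpoints are pre- versus post-vaccination responses in the same subjects, but the primary analysis in XII.2 states only between-group comparisons and no analysis of within-subject change

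*Protocol*

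**What the plan says.** Protocol VI.1 (Study Endpoints), repeated in the Study Summary: "The primary study endpoints will be determination of pre and post vaccination immune responses in 26 healthy human subjects". The Study Design and Methodology paragraph of the Study Summary adds: "Humoral, cellular and secretory immune responses will be measured 2 and 4 weeks after each vaccine dose and compared with baseline values".

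The Primary Analysis in XII.2 has two branches. For normally distributed data it gives geometric means and standard deviations, "and the vaccine groups compared using parametric tests". Otherwise it gives medians with ranges, and "comparison between groups will then be by non-parametric tests". Neither branch mentions change from Day 0 or a paired comparison, and neither says whether raw values or changes enter the group comparison.

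Under Secondary Analyses, XII.2 sets the level: "All statistical tests will be performed using a 5% significance level, leading to 95% confidence intervals". XII.1 fixes the arm sizes ("The sample size of 8 subjects in arms 3 and 4 and 5 in arms 1 and 2"), calls the study descriptive and says that its size does not come from a power calculation.

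**The concern.** The endpoint asks whether a subject's response rose after vaccination. The stated analysis asks whether the arms differ. If all four regimens raised responses equally, a between-arm comparison would show no difference and would leave the primary endpoint unanswered. Objectives 2 and 4 (inhibiting antibody and T-cell responses after vaccination) need the pre/post contrast; objective 1 (augmentation by prime boost) needs the between-arm one. XII.2 provides for the second only.

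Two things are at stake. An analyst who has only XII.2 might apply its group summaries or independent-group tests to Day 0 versus a later visit, so that variation between subjects enters the error. Or within-arm tests might be added without a rule and then compared across arms of unequal size.

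**Working it through.** **1. The contrast.** Each subject gives serum and nasal wash on Day 0 and at five later visits (Days 14, 28, 56, 70 and 84), and cells on Days 0, 14 and 70 (VI.10.1.3). Day 0 and later values therefore come from the same subject. Set side by side:

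| Place | Contrast |
|---|---|
| VI.1, primary endpoints | before v after vaccination, same subjects |
| Study Summary, design paragraph | 2 and 4 weeks after each dose v baseline |
| XII.2 Primary Analysis, both branches | vaccine group v vaccine group |
| XII.2 Secondary Analyses | adverse events between doses and between vaccines |

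The comparison of adverse events between doses is the only one in XII.2 that could be within-subject, and it is not an immune response.

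**2. The plan's own figure.** Subjects randomised: 5 + 5 + 8 + 8 = 26, as stated. There is no power figure to reproduce.

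**3. What pairing is worth.** The protocol gives no SD or correlation. Assumptions: log2 titre SD 1.5 at both times, two-sided 5%. The SD of a subject's change is SD × √(2(1 − ρ)). At ρ = 0.5 it is 1.5 × √1 = 1.5; at ρ = 0 it is 1.5 × √2 = 2.12. Simulated power for the pre/post rise:

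| n | True rise | ρ | Paired t | Independent t |
|---|---|---|---|---|
| 8 | 4-fold | 0.5 | 90% | 75% |
| 5 | 4-fold | 0.5 | 62% | 46% |
| 26 | 2-fold | 0.5 | 91% | 71% |
| 8 | 2-fold | 0.3 | 28% | 21% |
| 8 | 2-fold | 0.8 | 73% | 13% |
| 5 | 4-fold | 0.3 | 48% | 46% |
| 8 | 4-fold | 0 | 63% | 70% |
| 8 | 4-fold | baseline constant | 90% | 93% |

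The last row matters for H5N1. The microneutralization section (VI.10.2.4) assigns a titre of 10 to sera negative at 1/20, and IV.7 considers prior H5N1 exposure unlikely in the subjects with strong cross-reactivity. Many baselines may therefore be equal, and pairing then gains nothing.

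**4. Attainable p-values.** For the between-group fallback that XII.2 does state, the smallest exact two-sided Mann-Whitney p is 2/C(n₁+n₂, n₁):
- 5 v 5: 2/252 = 0.0079
- 5 v 8: 2/1287 = 0.0016
- 8 v 8: 2/12870 = 0.00016

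All are below 5%. For an exact two-sided signed-rank test within one arm, which XII.2 does not name, the minimum is 2/2ⁿ: 2/32 = 0.0625 at n = 5 and 2/256 = 0.0078 at n = 8. At n = 5 the uncorrected normal approximation gives 0.043 and the corrected one 0.059.

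**The case against.** The strongest reply is that XII.2 is silent rather than wrong. It does not say which values enter the group comparison, changes from baseline would use the pairing, the Study Summary does promise comparison with baseline, and the choice of test can be left to an analysis plan. Much of this stands: that pairing goes unused is something a reader might infer, not something the protocol says. But XII.2 does not defer the matter. It fixes a primary analysis, and even a between-arm comparison of changes would not estimate the rise itself.

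A second reply is that this is a descriptive pilot, and that objective 2 can be met by describing titres. That limits the consequence. It does not remove it, because the primary endpoint still needs a stated summary of change and XII.2 applies "All statistical tests will be performed using a 5% significance level".

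A reader might also infer that the non-parametric fallback can never reach 5% in the 5-subject arms, and that the plan is therefore tilted toward the heterologous regimens. The documents do not support this. The fallback is stated only between groups, where 5% is attainable; no signed-rank test is named; and exactness is not fixed. The pattern would arise only if someone compared arms by their own within-arm significance, whereas XII.2 compares the groups directly.

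**Conclusion.** The mismatch holds: the primary analysis as written does not address the pre/post contrast that defines the primary endpoints. It should be corrected, and the scale of the problem is moderate. The possible loss of power ranges from large (73% v 13% for a 2-fold rise at n = 8 and ρ = 0.8) to none (ρ near 0, or baselines at the floor), all under an assumed log2 SD of 1.5. The main conclusion does not rest on these figures; it follows from setting VI.1 beside XII.2.

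The 0.0625 minimum is a caution only. It applies if an exact two-sided signed-rank test is used on two time points within a 5-subject arm. Since the 5-subject arms are both autologous and the 8-subject arms both heterologous, within-arm significance must not be compared across arms.

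**What to change.** In XII.2, Primary Analysis, state that:
- pre/post comparisons use each subject's own change from Day 0;
- for titre endpoints, the result is the geometric mean fold rise with 95% CI from paired log titres, per arm and over all 26, with individual changes shown for the small arms;
- for the T-cell percentage and M2e staining endpoints, which are not titres, a paired change on a scale suited to each is used;
- a claim that one regimen augments responses more than another rests on the between-arm comparison of baseline-referenced responses, not on which arm's own rise is significant.

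If a signed-rank test is kept within arms, note its minimum p at n = 5 and n = 8.

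The cost is wording only; no new data or visits are needed. The downside is small: the paired interval relies on approximately normal log changes in arms of 5 to 8, which is doubtful where many values sit at the assay floor, and there the gain in precision is also small or nil.
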